7.1.2 QTc Stopping Criteria

There is no preclinical or clinical evidence that balovaptan administration may be associated with an increase in the corrected QT interval (QTc).

Nevertheless, treatment should be discontinued in case of the following:

- Sustained (at least two ECG measurements >30 minutes apart) QTcF that is >500 ms and/or >60 ms longer than the baseline value

Treatment with balovaptan should be discontinued in participants who develop changes in QT interval, as described in [Appendix 6](#). ECG assessment should be conducted as outlined in Section [8.2.4](#).

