7.1 DISCONTINUATION OF STUDY TREATMENT

It may be necessary for a participant to permanently discontinue (definitive discontinuation) study treatment. If study treatment is definitively discontinued, the

participant will remain in the study for additional assessments. Refer to the schedule of activities (see Section 1.3) for data to be collected at the time of discontinuation of study treatment and for any further follow-up evaluations that need to be completed.

Participants must permanently discontinue study treatment if they experience any of the following:

- Any medical condition that the investigator or Sponsor determines may jeopardize the participant's safety if he or she continues to receive study treatment
- Investigator or Sponsor determination that treatment discontinuation is in the best interest of the participant
- Pregnancy
- Inability of participant to continue to comply with study requirements
- Suicidal ideation score of 4 or 5 or category 6 or greater on the C-SSRS
- Specific events that are described in Sections 7.1.1, 7.1.2, 7.1.3, and 7.1.4

The primary reason for study treatment discontinuation should be documented on the appropriate eCRF.

All participants who withdraw or discontinue from the study treatment early will be asked to return as soon as possible (and within 2 weeks after the last dose of study drug) for an early discontinuation visit and complete the assessments as per the schedule of activities in Section 1.3 (see Table 1). Participants will also be asked to return for assessments of the primary and secondary efficacy outcomes at the end of the 12-week planned visit, regardless of their adherence to treatment. If the time between the early discontinuation visit and the 12-week planned visit is fewer than 2 weeks, then participants are exempted from the 12-week planned visit. If the time between the early discontinuation visit and the previous visit is fewer than 2 weeks, then participants are exempted from completing again all the primary and secondary assessments at the early discontinuation visit.

Refer to the schedule of activities in Section 1.3 (see Table 1) for details on follow-up assessments to be performed for participants who permanently discontinue study treatment. If a participant requests to be withdrawn from treatment or follow-up assessments, this request must be documented in the source documents and signed by the investigator.

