If at a particular postdose timepoint the mean QTcF is > 500 ms and/or > 60 ms longer than the baseline value, another ECG must be recorded, ideally within the next 30 minutes, and ECG monitoring should continue until QTcF has stabilized on two successive ECGs. The Medical Monitor should be notified. Standard-of-care treatment may be instituted at the investigator's discretion. If a PK sample is not scheduled for that timepoint, one should be obtained. A decision on study drug discontinuation should be made, as described in [Appendix 6](#) (see Section [A6–2.7](#)). The investigator should also evaluate the participant for potential concurrent risk factors (e.g., electrolyte abnormalities, concomitant medications known to prolong the QT interval, severe bradycardia).

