Appendix 6: Safety Plan: Management of Identified and Potential Risks

In the event of reports matching the related adverse events of special interest definition (see Section 8.3.7), participants should be evaluated for use of any concomitant medication as well as occurrence of any recent accidents or physical exercise. In the event that CPK values exceed $10\times$ ULN, confirmatory samples should be obtained within 3–5 days, depending on the actual CPK value and circumstances, for example, whether or not a possible alternative explanation like an accident or sports is present. Serum creatinine and serum potassium levels should be measured at the same time. An ECG recording may provide information about QRS complex changes and arrhythmias potentially related to changes in potassium.

Hydration status should be assessed and intake of fluids is advised. The need for hospitalization and intravenous administration of fluids, respectively, should be considered, depending on the CPK increase and a participant's hydration status. The investigator may decide to temporarily withdraw treatment if no alternative explanation exists and CPK values do not show a trend for normalization according to the half-life of CPK in plasma. Treatment may be re-started once CPK values have shown a clear trend toward normalization and if CPK increases were not associated with relevant kidney dysfunction. CPK levels should be monitored until they are below $2\times$ ULN or in the range of screening and baseline values.

CPK laboratory abnormality as per Section 8.3.7 must be reported as an adverse event of special interest.

CPK values will be assessed at baseline, at Week 6 and Week 12 (see the schedule of activities in Section 1.3 [see Table 1]) as well as at the post-treatment follow-up visit.

A6–2.7 MANAGEMENT OF CARDIAC ADVERSE EVENTS

Increases in the Corrected QT Interval (QTc) Interval

There is no preclinical or clinical evidence that balovaptan administration may be associated with an increase in the QTc interval. Nevertheless, treatment should be discontinued in case of the following:

- Sustained (at least two ECG measurements >30 minutes apart) QT interval corrected through use of Fridericia's formula (QTcF) that is >500 ms and >60 ms longer than the baseline value. In this instance, serum electrolytes, in particular, potassium, and magnesium, as well as use of any concomitant medications should be analyzed as a potential cause of the increase in the QTc interval.

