Management of participants with sustained QTc prolongation should include close monitoring, with ECGs repeated until two successive ECGs show resolution of the findings, correction of any electrolyte abnormalities, and possible discontinuation of other concomitant medications that are known to prolong the QTc interval. Consultation with a

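### The QTcF stopping rule needs either condition in Section 7.1.2 but both in Appendix 6 (A6-2.7), where Section 8.2.4 sends the discontinuation decision

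*Combined protocol and SAP*

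**What the plan says.** Section 7.1 opens its list with "Participants must permanently discontinue study treatment if they experience any of the following", and the last item on that list names Section 7.1.2. Section 7.1.2 calls for discontinuation on a sustained "QTcF that is >500 ms and/or >60 ms longer than the baseline value", where sustained means at least two ECGs more than 30 minutes apart. It then points to Appendix 6: "Treatment with balovaptan should be discontinued in participants who develop changes in QT interval, as described in" that appendix.

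Appendix 6, Section A6-2.7, introduces its rule in the same way and defines sustained in the same way, but its criterion is a QTcF "that is >500 ms and >60 ms longer than the baseline value".

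Section 8.2.4 covers ECG conduct. Its trigger for a repeat recording is that "the mean QTcF is > 500 ms and/or > 60 ms longer than the baseline value, another ECG must be recorded". It then says "A decision on study drug discontinuation should be made, as described in" Appendix 6, and cites Section A6-2.7 specifically.

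All three are current protocol text. The QTcF change in the amendment summary concerns only the exclusion criterion in Section 5.2. Nothing in the protocol says which version of the stopping rule governs.

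**The concern.** The protocol states one safety decision twice, with different thresholds. Under Section 7.1.2 an absolute QTcF above 500 ms or a rise of more than 60 ms is enough. Under A6-2.7 neither is enough alone.

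A site that has just recorded a prolonged QTcF will be working from Section 8.2.4, which leads it to A6-2.7. If it applies only the criterion found there, it can keep dosing a participant whom Section 7.1.2 says should stop. Two sites with identical tracings could act differently, each citing the protocol, and the one that continued would be out of compliance with Section 7.1.2.

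No estimand, sample size or error rate is affected. What is at stake is participant safety and consistent conduct across sites.

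**Working it through.** The documents give no figure to reproduce. The check compares the two rules as written and works out where they part.

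**Inputs**
- Section 7.1.2: stop if sustained QTcF > 500 ms or QTcF − B > 60 ms, where B is the baseline.
- A6-2.7: stop if sustained QTcF > 500 ms and QTcF − B > 60 ms.
- Section 5.2: a confirmed screening QTcF of 450 ms or more (men) or 470 ms or more (women) is excluded.
- The baselines below are illustrations; the documents give no QTcF distribution.

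**Thresholds**
- Section 7.1.2 stops above min(500, B + 60).
- A6-2.7 stops above max(500, B + 60).
- Gap = |500 − (B + 60)| = |B − 440| ms.

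| Baseline B (ms) | B + 60 | 7.1.2 stops above | A6-2.7 stops above | Gap | Rise needed, 7.1.2 | Rise needed, A6-2.7 |
|---|---|---|---|---|---|---|
| 380 | 440 | 440 | 500 | 60 | > 60 | > 120 |
| 400 | 460 | 460 | 500 | 40 | > 60 | > 100 |
| 420 | 480 | 480 | 500 | 20 | > 60 | > 80 |
| 440 | 500 | 500 | 500 | 0 | > 60 | > 60 |
| 460 | 520 | 500 | 520 | 20 | > 40 | > 60 |

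**Reading the table**
- Below 440 ms, a QTcF above 500 ms already implies a rise of more than 60 ms. The 60 ms condition therefore does nothing in A6-2.7, and the rule reduces to QTcF > 500 ms.
- Above 440 ms, a rise of more than 60 ms already implies QTcF above 500 ms. The 500 ms condition then does nothing, and the rule reduces to a rise of more than 60 ms.

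**Discordant cases**
- B = 400, sustained 490: rise 490 − 400 = 90, not above 500. Section 7.1.2 stops; A6-2.7 does not.
- B = 420, sustained 485: rise 485 − 420 = 65, not above 500. Section 7.1.2 stops; A6-2.7 does not.
- B = 460, sustained 505: above 500, rise 505 − 460 = 45. Section 7.1.2 stops; A6-2.7 does not. A screening value of 460 ms is eligible for women but not for men.

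**Direction.** Any QTcF that meets both conditions also meets at least one, so every A6-2.7 stop is a Section 7.1.2 stop. The discordance runs only towards continuing treatment under A6-2.7.

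**Which wording is the outlier.** Two of the three statements of these thresholds (the stopping rule in Section 7.1.2 and the trigger in Section 8.2.4) use *and/or*. The mandatory list in Section 7.1 names Section 7.1.2 and not Appendix 6. Only A6-2.7 uses *and*.

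**The case against.** The strongest reply is that the two rules can be followed together. A6-2.7 lists a narrower set of cases but nowhere tells a site to continue outside it, so a site that obeys Section 7.1.2 satisfies both. Harm requires someone to overlook the section devoted to QTc stopping and use the appendix alone. That is correct as logic. But Section 8.2.4 directs the decision to A6-2.7, so using the appendix alone is a natural reading.

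Second, discordant cases would not go unnoticed. Each has already met the trigger in Section 8.2.4, after which "ECG monitoring should continue until QTcF has stabilized on two successive ECGs. The Medical Monitor should be notified". A6-2.7 adds "close monitoring, with ECGs repeated until two successive ECGs show resolution of the findings", correction of electrolytes and a recommended cardiology consultation. Section 7.1 also requires stopping whenever the investigator or Sponsor judges it necessary for safety. This stands and limits the consequence. Monitoring does not, however, say whether to stop, which is the question the criterion exists to answer.

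Third, the rule will seldom act. The thorough QT study described in A6-1.4 found no QTc prolongation at 10 mg or 50 mg, about 30 participants are planned (15 per arm), and Week 2 is the only scheduled post-baseline ECG with substantial treatment left to stop. The screening limits also bound the effect on the 500 ms condition: if baseline is close to the screening value, A6-2.7 moves it by less than 10 ms in men (450 − 440) and less than 30 ms in women (470 − 440). All of this stands. The discordance is mainly in the 60 ms condition.

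Fourth, placing the error in A6-2.7 is an inference. The Section 7.1 list also names Section 7.1.3, where discontinuation is only suggested, so being on the list does not settle the matter. The agreement between Sections 7.1.2 and 8.2.4 still makes *and/or* the likelier intent, and it is the safer choice.

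The prompt repeat ECG, ideally within 30 minutes, also sits awkwardly with a definition of sustained that needs more than 30 minutes. That is a separate matter and leaves this conflict as it is.

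**Conclusion.** The concern holds, and it should be fixed. The criterion in A6-2.7 is too narrow and contradicts Section 7.1.2 for every baseline other than 440 ms, by |B − 440| ms: 40 ms at a baseline of 400 and 20 ms at 420 or 460. The error runs in one direction, towards continued dosing.

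The practical consequence is modest. It is confined to the discontinuation decision, in a drug with a negative thorough QT study and a trial with about 15 participants on balovaptan, and any affected participant would be detected and followed. The documents give no QTcF variance, so no probability of a discordant case is offered. The threshold comparison rests only on the protocol's wording. Treating *and/or* as the intended rule rests on its use in two of the three places and on the Section 7.1 list.

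**What to change.** In Appendix 6, Section A6-2.7, replace *and* with *and/or* between the 500 ms and 60 ms conditions, so that it matches Section 7.1.2 and the trigger in Section 8.2.4. Resolving this conflict needs no other change of text.

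The cost is one word, made by amendment or by a letter to sites. It adds no visits, ECGs or analyses. The downside is at most a rare additional treatment discontinuation, which Section 7.1.2 already calls for.

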7.1.3 Hematological Toxicity Criteria

Treatment discontinuation is suggested for participants who meet the following criterion for decreased absolute neutrophil count (ANC):

If the ANC falls <800/ μ L and the low ANC is confirmed in a second sample to be obtained within about 3 working days. If the ANC is <800/ μ L for the second sample, the investigator should consider treatment discontinuation.

In cases of ANC related–treatment discontinuation, additional laboratory parameters should be considered by the Investigator, including fibrinogen, high-sensitivity C-reactive protein (hs-CRP), and check for anti-neutrophil cytoplasmic antibody (ANCA).

7.1.4 Cardiac Toxicity

Management guidelines and treatment discontinuation for cardiac events are provided in [Table 4](#).

Table 4 Management Guidelines for Cardiac Events

Cardiac Biomarker Result	Actions
hs-cTnT elevated above ULN	
 • If increased to more than 50 pg/mL, permanently stop treatment and manage as cardiac emergency • If increased to above ULN and by more than 50% compared with baseline: 
 – Check for cardio-vascular adverse events as soon as possible. – Perform 12-lead ECG as soon as possible. – Repeat cardiac biomarker testing, including troponin T, NT-proBN, and troponin I panel within 3 days of availability of results. – If repeat sample cannot be obtained within 3 days, treatment must be interrupted until repeat test results are available. • If increased to above ULN and by less than 50% compared with baseline: 
 – Repeat cardiac biomarker testing, including troponin T, NT-proBNP, and troponin I panel, within 1 week of availability of results. – Perform 12-lead ECG within 1 week of availability of results. – If repeat sample cannot be obtained within 1 week, treatment must be interrupted until repeat test results are available.
Repeat blood sample	
 • If hs-cTnT has further increased or stays above ULN with 50% increase relative to baseline: 
 – Permanently discontinue treatment. – Perform 12-lead ECG. – Refer participant to local cardiologist consultant and cardiologist consult should include Doppler echocardiogram, including assessment of systolic and diastolic ventricular wall function. • If hs-cTnT is above ULN but has not further increased plus hs-cTnT value is less than baseline value plus 50% of baseline value: 
 – Interrupt study treatment. – Perform 12-lead ECG. – Refer participant to cardiologist consultant and cardiologist consult should include Doppler echocardiogram, including assessment of systolic and diastolic ventricular wall function. – Consider-restart of treatment with tight hs-cTnT monitoring with local cardiologist consult. • If hs-cTnT has returned below ULN, no further activity is needed and treatment can continue.

hs-cTnT=high-sensitivity cardiac troponin T; NT-proBNP=N-terminal prohormone of brain natriuretic peptide; ULN=upper limit of normal.

7.1.5 Peripheral Neuropathy

Signs and symptoms suggestive of peripheral neuropathy should promptly be followed up to confirm or disprove suspicion and to check for alternative explanations

other than study treatment. Follow-up activities may include electro-physiological examinations, temporary treatment hold, and a consultancy by an expert to diagnose peripheral neuropathy in humans.

Should the suspicion of peripheral neuropathy be verified and no alternative explanation known, study treatment should be discontinued permanently.

7.2 PARTICIPANT DISCONTINUATION OR WITHDRAWAL FROM THE STUDY

A participant may withdraw from the study at any time at his or her own request, or may be withdrawn at any time at the discretion of the investigator for safety, behavioral, compliance, or administrative reasons.

The primary reason for discontinuation from the study should be documented on the appropriate eCRF. If a participant requests to be withdrawn from the study, this request must be documented in the source documents and signed by the investigator.

At the time of discontinuing from the study, if possible, an early discontinuation visit should be conducted, as shown in the schedule of activities (see Section 1.3). Refer to the schedule of activities for data to be collected at the time of study discontinuation and follow-up and for any further evaluations that need to be completed.

The participant will be permanently discontinued both from the study treatment and from the study at that time.

If a participant withdraws consent from the study, the Sponsor may retain and continue to use any data collected before withdrawal of consent. Samples collected prior to withdrawal may be analyzed, unless the participant specifically requests that the samples be destroyed (as documented in the source documents) or local laws require destruction of the samples. However, if samples have been tested prior to withdrawal, results from those tests will remain as part of the overall research data.

7.3 PARTICIPANTS LOST TO FOLLOW-UP

A participant will be considered lost to follow-up if he or she repeatedly fails to return for scheduled visits and is unable to be contacted by the study site.

The following actions must be taken if a participant fails to return to the clinic for a required study visit:

- The site must attempt to contact the participant and reschedule the missed visit as soon as possible and counsel the participant on the importance of maintaining the assigned visit schedule. If the participant is unable or unwilling to comply with study visits, site personnel should assess reasons the participant is unable or unwilling to return to the clinic, and determine if there are ways to support participant participation.

- Before a participant is deemed lost to follow up, the investigator or designee must make every effort to regain contact with the participant (where possible, three telephone calls and, if necessary, a certified letter to the participant's last known mailing address or local equivalent methods). These contact attempts should be documented in the participant's medical record.
- Should the participant continue to be unreachable, he or she will be considered lost to follow-up and will be withdrawn from the study.

Discontinuation of specific sites or of the study as a whole are handled as part of [Appendix 1](#).

8. STUDY ASSESSMENTS AND PROCEDURES

Written informed consent for participation in the study must be obtained before performing any study-related procedures (including screening evaluations). Informed Consent Forms for enrolled individuals and for individuals who are not subsequently enrolled will be maintained at the study site.

Study procedures and their timing are summarized in the schedule of activities (see Section [1.3](#)). Protocol waivers or exemptions are not allowed.

Immediate safety concerns should be discussed with the Sponsor immediately upon occurrence or awareness to determine if the participant should continue or discontinue study treatment.

Adherence to the study design requirements, including those specified in the schedule of activities, is essential and required for study conduct.

All screening evaluations must be completed and reviewed to confirm that potential participants meet all eligibility criteria. The investigator will maintain a screening log to record details of all participants screened and to confirm eligibility or record reasons for screening failure as applicable.

Medical history and baseline conditions, including clinically significant diseases, surgeries history and baseline conditions, including clinically significant diseases, surgeries, cancer history (including prior cancer therapies and procedures), reproductive status, smoking history, and use of alcohol and drugs of abuse will be recorded at baseline. Any medication and/or vaccine (including over-the-counter or prescription medicines, vitamins, and/or herbal supplements) used by the participant within 24 weeks prior to the screening visit will be recorded at baseline. Demographic data, including age, sex, and self-reported race/ethnicity, will also be recorded. At the time of each follow-up physical examination, an interval medical history should be obtained and any changes in medications and allergies should be recorded.

Participants will be closely monitored for safety throughout the study. For in-clinic visits, participants should be assessed for toxicity prior to each dose; treatment will be administered only if the clinical assessment and local laboratory test values are acceptable. Urgent safety concerns should be discussed with the Sponsor immediately upon occurrence or awareness to determine if the participant should continue or discontinue study treatment.

8.1 EFFICACY ASSESSMENTS

8.1.1 Clinical Outcome Assessments

Participant-reported outcomes (PRO), clinician-reported outcomes (ClinRO) and performance outcome (PerfO) instruments will be completed to assess the treatment benefit of balovaptan.

PRO data will be collected through use of the following instruments: Life Events Checklist for DSM-5 (LEC-5), PCL-5, Patient Health Questionnaire-9 (PHQ-9), Beck Anxiety Inventory (BAI), Pittsburgh Sleep Quality Index (PSQI), Sheehan Disability Scale (SDS), Cognitive and Physical Functioning Questionnaire (CPFQ), Patient-Global Impression of Severity (PGI-S), and Patient-Global Impression of Change (PGI-C).

ClinRO data will be collected through use of the following instruments: SCID-5, CAPS-5, Clinician-Global Impression of Severity (CGI-S), and Clinician-Global Impression of Change (CGI-C).

PCL-5 and LEC-5 are the PROs completed at screening, as well as the SCID-5 (ClinRO). The recommended order for administration is: PCL-5, SCID-5, and LEC-5. For all other visits, PROs must be completed before the ClinROs in the following order: PHQ-9, PCL-5, PSQI, BAI, CPFQ, SDS, PGI-S, PGI-C. ClinROs should be completed, starting with the CAPS-5, CGI-S, followed by the CGI-C.

Clinician-Administered PTSD scale for DSM-5 (CAPS-5) is the clinical outcome assessment that will be used to determine the primary endpoint (see [Table 2](#) and Section 9.4.2). CGI-S and PHQ-9 are the clinical outcome assessments that will be used to determine the secondary endpoints (see [Table 2](#) and Section 9.4.3). For any individual patient, the CGI-S/C should be completed by the same rater throughout the study.

PerfO data will be collected through the use of a computerized cognitive battery.

